### ***Biostatistical Analysis***

#### **Sample Size:**

We estimated study size based on postoperative pain scores in a recent study of surgical patients at our institution (manuscript submitted); mean NRS was  $50 \pm 28$ . Our estimate for effect size is based on published data showing that a difference in NRS of 20/100 points is clinically significant. A sample size of 32 per group will have 80% power to detect a difference in means of 20 (the difference between a Group 1 mean,  $m_1$ , of 50 and a Group 2 mean,  $m_2$ , of 30) assuming the common standard deviation is 28 using a two group t-test with a 0.05 significance level. To account for dropout, we will enroll an additional 8 patients for each group for a total sample size of 80 patients.

Statistical Analysis:

Data will be summarized using descriptive statistics and will be presented as means (SD), medians [IQR] or frequency counts (%), as appropriate. Data will be analyzed on an intention to treat basis. We will first examine the success of randomization by comparing covariates demographic and clinical covariate measurements between the FULL-BUP and STD-BUP groups; to conserve study power, no formal statistical comparison will be performed and the data will be reviewed visually. Next we will perform univariate analyses to compare outcome measures between the FULL-BUP and STD-BUP groups, using a two-sided t-test or Mann Whitney U test for continuous variables and chi square or Fisher exact tests for categorical data, as appropriate. For paired analysis of pre/post surgery instruments, we will use McNemar's test or the Wilcoxon test, as appropriate. We will then explore the relationships between demographic and clinical variables and outcome measures in bivariate analyses, using the above methods or Pearson's and/or Spearman's correlation, ANOVA or Kruskal-Wallis test, as appropriate. Finally, we will explore further any observed differences in outcome measures between study arms by adjusting for covariates using analysis of covariance or (in the event of missing data), mixed models regression. Covariates will be entered into the model if they demonstrate a significant ( $p \leq 0.1$ ) association with outcome measures in bivariate analyses.

We will perform an interim analysis at 50% enrollment and will terminate the study if a significant pain score difference is detected. Significance for the interim analysis will be accepted at  $p < 0.003$ , based on 2 sequential tests and using an O'Brien-Fleming spending function to determine test boundaries. Significance overall will be accepted at  $p < 0.047$  to account for interim analysis. All statistical analyses will be performed by the Navigation team at CORE using SPSS Statistical Software version 27 (IBM SPSS Inc., Armonk, NY).

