#### Measures for Aim 1 (Pain scores)

The primary outcome of this study will be composite pain scores 24 hours after surgery. Others have shown that composite pain scores quantify pain with greater accuracy than a single measurement. Jensen et. al. concluded in their study that composite pain intensity scores from two or more individual ratings of pain are valid for detecting treatment effects. Pain scores will be measured using a numeric rating scale (NRS) (0=no pain; 10= worst possible pain). "Worst," "average," and

“least” pain scores will be assessed for the preceding time interval at 24, 48, and 72 hours following surgery. Inpatient pain scores will be collected as part of routine post-operative care and will be extracted from the medical record; there is no set protocol for routine pain score collection but typically it is done every 4-8 hours. To collect pain scores, nursing staff asks patients to rate their current pain on a scale from 0-10. If a participant is discharged prior to 72 hours after surgery, NRS scores will be assessed at the remaining time points via telephone. Prior to discharge, study staff will provide patients with a log to keep a record of their pain scores, at least once every 8 hours, in order to mitigate recall bias in anticipation of being contacted by research staff. Study staff will call discharged patients and ask them to report their pain scores for each 24 hour period between discharge and 72 hours postoperatively as recorded on the forms they were given at time of discharge.

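### The between-arm comparison of the primary outcome can use only patients with a 24-hour pain score, and the plan's one missing-data method is a late, conditional step that does not reach it

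*Combined protocol and SAP*

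**What the plan says.** Under Measures for Aim 1 (Pain scores): "The primary outcome of this study will be composite pain scores 24 hours after surgery". Worst, average and least pain are also assessed at 48 and 72 hours.

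Under Biostatistical Analysis, the population statement is "Data will be analyzed on an intention to treat basis", with no further definition of the analysis set. Outcomes are then compared between arms "using a two-sided t-test or Mann Whitney U test for continuous variables". Missing data are mentioned once, in the last analysis step: "Finally, we will explore further any observed differences in outcome measures between study arms by adjusting for covariates", with the method given as "using analysis of covariance or (in the event of missing data), mixed models regression".

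The sample size is 32 per group for a two-group t-test. On losses it says "To account for dropout, we will enroll an additional 8 patients for each group", which makes 80 in total.

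In the text available for review, where a short part after the statistical section is missing, there is no imputation rule, no sensitivity analysis for missing scores, and no rule for a randomised patient without a 24-hour score.

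**The concern.** A t-test or a Mann-Whitney test needs an observed value from each patient. With no imputation stated, a randomised patient without a 24-hour score is left out of the comparison that answers the primary question. The mixed model does not repair this, for three reasons.

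- It comes after the primary comparison and is described as exploratory.
- It follows only when a difference has been seen. If missing scores hide a difference, it is not triggered.
- If it is fitted to the 24-hour score alone, each patient has one record and the same patients are lost. It helps only if later scores enter as repeated measures, which the plan does not say.

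What is at stake is bias rather than power. The trial is unblinded, patients may withdraw at any time, and the Limitations section says that randomisation takes place before admission. A patient can therefore learn the assignment and leave, or have surgery cancelled, before any score exists. If that happens for different reasons in the two arms, the patients analysed are no longer the groups that were randomised.

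**Working it through.** **Inputs.** From Sample Size: difference 20 and SD 28 on a 0-100 scale, two-sided alpha 0.05, 80% power, 32 per group plus 8 for dropout. From the interim-analysis paragraph: final significance level 0.047. The documents give no missingness pattern, so the missing fractions and gaps below are assumptions.

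**1. The plan's figures.** With a standardised difference of 20/28, the noncentral t solution is 31.76, rounded up to 32 per group. Power at 32 is 80.3% at 0.05. Then 32/(1 - 0.20) = 40 per group, 80 in total. The plan's figures reproduce.

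**2. Who may be outside the test.** 8/40 = 20% per arm, or up to 16 of 80 patients if every budgeted dropout lacked a 24-hour score.

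**3. Power.** At 0.047, power is 79.5% with 32 per group analysed and 87.8% with all 40. The loss is already paid for in the sample size. The 87.8% is a ceiling, because a model or imputation recovers only part of the lost information.

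**4. Bias.** Let m be the fraction missing in an arm and g the mean gap between its missing and observed patients. The all-patient mean is (1 - m) × observed mean + m × (observed mean + g), so leaving out the missing patients shifts that arm's mean by m × g in size. The shift in the treatment difference is the difference of the two arms' m × g.

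| Assumed loss | g = 10 | g = 28 (one SD) | Share of the 20-point target |
|---|---|---|---|
| 10% missing, informative in one arm only | 1.0 | 2.8 | 5% to 14% |
| 20% missing, informative in one arm only | 2.0 | 5.6 | 10% to 28% |
| Equal m and equal g in both arms | 0 | 0 | 0% |

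**5. Effect on the decision at the unfavourable end.** This is an illustrative simulation with 40 per arm and 10,000 trials. About 20% are missing in each arm, at random in STD-BUP and more often with higher pain in FULL-BUP. A true difference of 20 is estimated as about 15, power at 0.047 falls from about 79% to 57%, and rejection with no true difference rises to about 10%.

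**6. What a repeated-measures model recovers.** This simulation has 40 per arm, SD 28, correlations 0.7, 0.6 and 0.7 among the three time points, 20% missing per arm, informative loss in one arm only, no true difference, and 2,000 trials per row. The strength of selection is assumed.

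| What drives the loss | Bias, observed 24-hour scores only | Bias, repeated-measures model |
|---|---|---|
| Later scores, which are observed | -4.3 | 0.0 |
| The 24-hour pain itself | -6.0 | -3.0 |
| Patient has no score at any time | -4.05 | -4.05 |

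The model removes all, half or none of the bias, depending on why scores are missing.

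**The case against.** The strongest reply is that few 24-hour scores will be missing. Inpatient scores come from the chart, typically every 4 to 8 hours. Patients who leave early keep a log and are telephoned, and each assessment is paid. Early discharge therefore does not by itself lose the score. The dropout allowance also covers a study with 30-day follow-up. This stands. A reader might infer that 20% of patients will be missing from the primary test, but the documents support 20% only as an upper working limit.

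Second, intention to treat can mean analysis by assigned arm, which both tests respect, and the plan never uses the term complete-case. This stands in part. A reader might infer that the intention-to-treat statement is simply false. The text shows something narrower: assignment is respected, but inclusion of all randomised patients is not secured. That the tests use observed scores only is an inference from the methods named and from a sample size that counts 32 evaluable patients per group.

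Third, a repeated-measures model may not help. Loss between randomisation and admission leaves no score at 24, 48 or 72 hours, and a population requiring at least one postoperative score excludes those same patients. This also stands. A reader might infer that the model would nearly abolish the bias, but that holds only when later observed scores explain the loss.

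None of these points supplies a missing-data provision for the primary comparison.

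**Conclusion.** The point holds in this form: patients are analysed by assigned arm, but those without a 24-hour score cannot enter the between-arm comparison, and the sole missing-data method is exploratory, conditional and unspecified as to later scores. The order and condition of that step are explicit in the text.

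The size is uncertain and may be small. Under loss that is informative in one arm only, with a gap of 10 to 28 points, the shift is 1.0 to 2.8 points at 10% missing and 2.0 to 5.6 points at 20%. It is 0 if both arms lose similar patients at similar rates. These are assumed patterns, not forecasts. The planned sample size does not need to change. The plan should be amended because the change is cheap and the protection it claims is not currently specified.

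**What to change.** - Define the intention-to-treat set as all randomised patients, in their assigned arm, and state how patients with no postoperative score (for example after cancelled surgery) are handled.
- Make the primary analysis a repeated-measures model of the 24-, 48- and 72-hour composite scores with arm, time, arm-by-time and the randomisation pain stratum. Fit it whether or not a difference is observed, and name the arm contrast at 24 hours as primary. Use the same model for the interim pain comparison.
- Keep the t-test as a supportive analysis of observed scores.
- Add a sensitivity analysis that imputes missing scores with shifts set separately by arm, over a stated range, and that includes randomised patients with no postoperative score. The repeated-measures model recovers information only for patients who miss the 24-hour score but have a later one, so this analysis must carry the others.
- Report missing 24-hour scores by arm and reason.

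The cost is analysis-plan wording and slightly more analysis work. The scores and the stratum are already collected, and standard software fits the model. The downside is a missing-at-random assumption in the primary model, which the shifted imputation tests.

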### ***Randomization Plan***

Enrolled participants will be randomized 1:1 into one of two groups (defined below). The randomization scheme will be developed using NQuery Software (Statistical Solutions, Boston, MA).and will use permuted blocks of 4 and 6 patients to ensure balance between study arms. The analyst will provide the research coordinator with randomization assignments in sequentially-numbered opaque envelopes (one series of envelopes for each stratum of anticipated post-surgical pain) . The study coordinator will pass the next envelope in sequence to another member of the study team when it is time to assign a subject to a group. Gerbershagen et. al. documented the distribution of pain scores for 179 different surgical procedures and we will use these data to establish randomization strata. For true practice generalizability on the association between buprenorphine management and postsurgical pain control, we will include surgical procedures based on average pain intensity on postoperative day (POD) 1, as opposed to limiting our criteria to a particular surgical type (see Appendix 1).

Patients will be stratified according to their anticipated pain score on POD 1 (4-6/10 range vs >6/10 range) and those within each stratum will be randomized to one of two groups as follows:

- FULL-BUP group: buprenorphine formulation continued throughout the perioperative period
- STD-BUP group: buprenorphine formulation reduced to 16mg the day prior to surgery and then 8mg on the day of surgery onwards. Participants in this group taking 12-16mg buprenorphine at baseline will have no change to their buprenorphine dose on the day prior to surgery.

All participants will be transitioned back to their regular dose of buprenorphine when postoperative surgical pain has subsided as determined by their

buprenorphine provider following hospital discharge. This transition will be coordinated with their buprenorphine provider, which is our current standard practice when buprenorphine is reduced perioperatively.

As the study is unblinded, both patients and providers will be aware of the randomization assignment. To help mitigate bias, the team members collecting and entering data will be masked regarding the patient's assignment. The REDCap database has the randomization assignments in an instrument separate from the study data collection instruments, allowing for data entry without seeing which group the subject is in.

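### The primary comparison ignores the pain stratum used to randomise; including it gains about 1 to 4 power points if strata differ by 10 to 20 points, at almost no cost

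*Combined protocol and SAP*

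**What the plan says.** The Randomization Plan sets up two strata: "Patients will be stratified according to their anticipated pain score on POD 1", with cut-offs of 4-6 and above 6 out of 10. Each stratum has its own allocation list ("one series of envelopes for each stratum of anticipated post-surgical pain"), in permuted blocks of 4 and 6. Appendix 1 assigns procedures to the strata.

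Under Biostatistical Analysis, the sample size rests on an unadjusted two-group t-test: "A sample size of 32 per group will have 80% power to detect a difference in means of 20", with SD 28 and a 0.05 level. For dropout, "we will enroll an additional 8 patients for each group for a total sample size of 80 patients". The outcome comparison between arms is made "using a two-sided t-test or Mann Whitney U test for continuous variables", again without a stratum term. Adjustment comes last, to "explore further any observed differences in outcome measures between study arms by adjusting for covariates". Entry to that model depends on the data: "Covariates will be entered into the model if they demonstrate a significant" association, at p ≤ 0.1, with the outcome. The interim paragraph sets the final level: "Significance overall will be accepted at" p < 0.047.

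The available text does not name the stratum as a model term. A short part of the document after the interim paragraph was not available for this review.

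**The concern.** The strata are defined by expected pain on the day after surgery, and the primary outcome is composite pain at 24 hours. The design therefore presumes that the stratum predicts the outcome.

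If it does, stratified allocation removes most between-stratum variation from the difference in arm means. A two-sample t-test does not know this: its standard error still includes that variation. The estimated standard error is too large, the true type I error falls below its nominal level, and power goes unused. The trial is sized at almost exactly 80% power, so even a few points for one line of SAP text are worth having.

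There is a second, smaller problem. A factor fixed by the design is left to a significance screen, so whether it is ever adjusted for depends partly on chance.

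**Working it through.** **Inputs from the plan.** Difference 20 and SD 28 on the 0-100 scale; 32 per group analysed; 40 per group enrolled; sizing level 0.05; final level 0.047; two strata; blocks of 4 and 6.

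**Assumptions.** The documents give neither the stratum gap D nor the share p in the severe stratum. D is taken from 0 to 20 points, and p as 50% or 30%.

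**1. The plan's own figure.** The standard error is 28 × √(2/32) = 7.0 and the noncentrality is 20/7.0 = 2.857. On 62 degrees of freedom the power is 80.3% (31 per group gives 79.0%). The stated 32 per group reproduces.

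**2. Closed form, strata exactly balanced across arms.** Hold the total SD at 28. The within-stratum SD is then √(28² − p(1−p)D²).

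- D = 10, p = 0.5: √(784 − 25) = 27.55.
- D = 20, p = 0.5: √(784 − 100) = 26.15. The true standard error is 26.15 × 0.25 = 6.54, against the 7.0 the t-test expects.

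At level 0.047 the critical value is 2.027. At D = 20 the unadjusted test in effect demands 2.027 × 28/26.15 = 2.170, which gives a type I error of about 0.034. Its power is 81.1%. The adjusted model, with noncentrality 20/6.54 = 3.06 on 61 degrees of freedom, has 84.7%, a gain of 3.6 points. At D = 10 the same steps give 79.9% and 80.8%, a gain of 0.9 points.

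**3. Simulation with dropout.** 20,000 trials per cell; 80 patients with random stratum membership, allocated in blocks of 4 and 6 within stratum; 64 retained at random; normal outcomes; one final look at 0.047. Monte Carlo standard error is about 0.0015 on type I error and 0.3 points on power.

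| Severe share | Gap | Type I error: t-test / with stratum | Power: t-test / with stratum |
|---|---|---|---|
| 50% | 0 | 0.048 / 0.048 | 79.5% / 79.2% |
| 50% | 10 | 0.044 / 0.048 | 79.4% / 80.3% |
| 50% | 15 | 0.040 / 0.046 | 80.0% / 82.0% |
| 50% | 20 | 0.034 / 0.044 | 80.7% / 84.5% |
| 30% | 10 | 0.046 / 0.049 | 79.6% / 80.3% |
| 30% | 20 | 0.039 / 0.047 | 80.2% / 83.8% |

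**4. Rank route, equal strata.** Power for Mann-Whitney and then its stratified form (van Elteren): gap 0, 77.4% and 76.5%; gap 10, 77.0% and 77.4%; gap 20, 78.3% and 81.9%.

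**5. Sensitivity, balanced strata, level 0.05.**

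- 25/75 stratum split, 32 per group: gains of 0.7 and 2.7 points at gaps 10 and 20.
- All 40 per group retained, equal strata: 0.6 and 2.3 points, on unadjusted power of 88.8% and 89.8%.
- 28 read as the within-stratum SD: 79.4% to 80.3% at gap 10, and 76.7% to 80.4% at gap 20.

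**6. The p ≤ 0.1 screen.** With a true 20-point treatment effect and equal strata, the stratum passes in about 38% of simulated trials at gap 10 and 89% at gap 20.

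**The case against.** The strongest reply is that nothing is broken. The sizing and the planned test agree, 32 per group delivers 80.3%, and the unadjusted test is valid and at worst conservative. That stands, and it is why this is an efficiency point.

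The size of the gain also rests on a gap the documents do not state. Patients receive multimodal analgesia, blocks and rescue as needed, so the realised gap may be smaller than the anticipated bands suggest. At a 5-point gap a rerun found no measurable gain. With 30% severe, repeat simulations put the 20-point gain between 2.8 and 3.6 points, and a 25/75 split with full retention brings the 10-point gain down to about 0.4. This also stands: the figure is conditional on the gap, the stratum mix and retention.

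The change is not costless on every route. The stratified rank test loses 0.9 points when the gap is 0 and gains only 0.4 at 10. That supports the linear model as the default.

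Finally, the exploratory model might pick up the stratum where it matters most. It usually would at a 20-point gap, but that analysis follows the primary test and cannot recover the primary test's power. At a 10-point gap the screen rejects the stratum more often than not.

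**Conclusion.** The concern holds. The primary comparison omits the factor by which the trial randomises. With roughly equal strata and 64 patients analysed, a linear model including it gains about 1 point of power at a 10-point gap and nearly 4 points at 20. It also brings the type I error closer to its nominal level (0.044 against 0.034 at gap 20). If the strata do not differ, the cost is about 0.02 points with exact balance and 0.2 to 0.3 points in simulation with random dropout.

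The direction is secure; the size depends on the assumed gap and stratum mix. The figures assume normal outcomes, a total SD of 28 and dropout at random, and they do not model the interim look.

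**What to change.** In the SAP, define the primary analysis of the 24-hour composite pain score as a linear model with arm and randomisation stratum, tested at the planned final level. State that the stratum stays in whatever its p-value and is exempt from the p ≤ 0.1 screen. Name the same model for the interim test.

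Use the stratum as randomised, by planned procedure. This needs saying because Appendix 1 lists laparoscopic procedures converted to open surgery in the severe group, and a conversion is known only after allocation.

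If a rank test is kept as a fallback, make it the van Elteren version, with the linear model as the default.

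The cost is a few sentences and one degree of freedom. No extra patients or data are needed, because the stratum is recorded at randomisation.

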### ***Study Procedures***

On the day of surgery, prior to the procedure, participants will be asked to complete a series of questionnaires to obtain baseline self-assessments for opioid cravings, opioid misuse, and opioid withdrawal symptoms (see protocol schema and Measures for Aim 3 section for details). Patients will be asked to report early for their procedure to complete the study questionnaires in a private space.

Both groups will receive identical preoperative, intraoperative and postoperative multimodal opioid sparing strategies, coordinated with the surgical, anesthetic, and psychiatric clinical care teams directly involved in the study participant's care. Multimodal analgesia, or the administration of two or more drugs that act by different mechanisms, provides more effective analgesia compared to medications used individually. Multimodal analgesia has been well established at achieving early recovery after surgery and reducing pain scores. According to the American Society of Anesthesiologists (ASA) task force for acute pain management, multimodal pain management therapies should be used for the treatment of surgical pain whenever possible however it is not mandatory to use these methods routinely for all surgical procedures and they are utilized at the discretion of the anesthesiologist taking care of the patient. As such, we will adopt this standard of care practice for the treatment of post-surgical pain in both randomized groups. Our multimodal analgesic strategy will consist of gabapentin, acetaminophen and Celebrex preoperatively and postoperative ketorolac, acetaminophen, opioids, nerve blocks infusions/epidural catheters, alpha agonists,

ketamine and lidocaine infusions as indicated. Postoperatively, opioid medications will be given IV or PO as second line analgesic agents. If a participant has an allergy or aversion to any of these medications, they will not receive the medication, but will be able to participate in the study with alternative medications. All analgesic medication administered will be documented by study staff. In the event of poorly controlled pain at any point during the study, we will provide the patient with appropriate analgesic rescue agents to ensure that post-surgical pain is adequately controlled.

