Intraoperative opioid consumption, type of anesthesia, total PACU opioid consumption, normalized for time spent in PACU, and 24, 48 up to 72-hour opioid consumption will be extracted from the patients' charts. All opioid consumption will be converted into MME. One month postoperatively, participants will receive virtually- administered questionnaires, including: a substance use evaluation, where they will be asked to complete self-assessments identical to those administered on the day of surgery for comparison analysis. Patients will be encouraged to record postoperative pain and opioid consumption on the Timeline website regularly and reminded that compensation is tied to completion. Reminder phone calls will be made by study staff during this time period.

We will contact each participant's buprenorphine provider to collect data for buprenorphine treatment retention following surgery and will assess each patient's Maine Prescription Awareness Tool (MainePAT) record to collect data for outpatient opioid utilization during the 30 days following surgery. Buprenorphine formulations will not be included in our MME total.

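### Adjusted models are fitted only for observed differences and select covariates by p≤0.1, so the adjusted estimate is data-dependent, selectively reported and not protected from post-assignment variables

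*Combined protocol and SAP*

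**What the plan says.** The Statistical Analysis text under Biostatistical Analysis sets out a sequence. The arms are first compared without adjustment, "using a two-sided t-test or Mann Whitney U test for continuous variables". Candidate covariates are then screened: "We will then explore the relationships between demographic and clinical variables and outcome measures in bivariate analyses". The last step is the adjusted model: "Finally, we will explore further any observed differences in outcome measures between study arms by adjusting for covariates using analysis of covariance", or mixed models regression if data are missing. The entry rule is "Covariates will be entered into the model if they demonstrate a significant" association, defined as p≤0.1.

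In the text available, there is no list of candidate covariates, no restriction to variables measured before randomisation, and no definition of an observed difference.

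Three other places bear on this:
- Randomization Plan: "Patients will be stratified according to their anticipated pain score on POD 1", in two strata (4-6 and above 6). The stratum is not named in any model.
- Study Procedures: the chart data to be extracted include "Intraoperative opioid consumption, type of anesthesia, total PACU opioid consumption, normalized for time spent in PACU".
- Study Procedures, on multimodal analgesic methods: "they are utilized at the discretion of the anesthesiologist taking care of the patient". The Randomization Plan states that providers know the assignment.

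**The concern.** There are two separate problems.

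**The condition.** An adjusted model is fitted where a difference has been seen and not otherwise. The set of adjusted results that gets reported then depends on the unadjusted results. The only provision for missing data found in the text, the mixed model, sits inside the same conditional step.

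**The screen.** Choosing covariates by their p-value against the outcome makes the model depend on the sample. A real baseline predictor can be dropped by chance, including the stratum, which is the one prognostic factor the protocol itself identifies. Irrelevant variables can enter. Because the candidate pool is not limited to baseline, variables recorded after assignment can also be screened. A variable of that kind that is affected by the arm and related to pain would tend to pass. Conditioning on it means the model no longer estimates the effect of assignment.

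At stake is the adjusted estimate and the weight a reader gives it beside the main test.

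**Working it through.** **Inputs from the plan.** 32 per group, difference 20, SD 28, two-group t-test at 0.05 (Sample Size); final level 0.047 (interim analysis paragraph); entry at p≤0.1. **Assumed inputs.** All covariate-outcome correlations (r), all arm shifts (a, in SD units) and the number of candidates. The documents give none of these, so ranges are shown.

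**1. The plan's own figure.** Standardised difference 20/28 = 0.714. The exact noncentral t gives n = 31.76, so 32 per group, with power 0.803 at level 0.05. The sample size reproduces. At level 0.047 the power is 0.795.

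**2. Chance of missing a real baseline predictor.** With N = 64, a two-sided p≤0.1 requires |r| ≥ t/√(62 + t²) with t = 1.670, which is 0.2075. By Fisher's z, P(miss) = Φ((atanh 0.2075 − atanh r)·√61). For r = 0.3 this is Φ((0.2106 − 0.3095)·7.81) = Φ(−0.77) = 0.22. Simulation (40,000 runs per setting) gives:

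| True r | Missed, N = 64 | Missed, N = 80 |
|---|---|---|
| 0.2 | 52% | 45% |
| 0.3 | 21% | 14% |
| 0.4 | 4% | 2% |
| 0.5 | 0.4% | 0.1% |

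**3. Noise variables.** Each irrelevant candidate enters 10% of the time. With 10 independent ones, P(at least one enters) = 1 − 0.9¹⁰ = 0.65.

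**4. Power, baseline covariates only.** Assume two real predictors with joint R² 0.20 (each r = √0.10 = 0.316) and 10 noise variables. Across repeated simulations at level 0.047, power is 0.79-0.80 unadjusted, 0.82-0.84 with the screen and 0.86-0.87 with the two predictors fixed in advance. As a check, the residual SD is 28·√0.80 = 25.0, which gives power 0.876 before the loss of degrees of freedom. The screen missed each real predictor about 20% of the time. Type I error was not inflated (4.5-5.0%).

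With a single fixed baseline covariate, taking the residual SD as 28·√(1 − r²), power is 0.811, 0.832, 0.860 and 0.896 for r = 0.2, 0.3, 0.4 and 0.5, against 0.795 unadjusted.

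**5. If a post-assignment variable entered.** Let the variable differ by a SD between arms and correlate r with pain within arm. The adjusted effect is then 20 − r × 28 × a.

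| Shift a | r = 0.3 | r = 0.5 |
|---|---|---|
| 0.25 | 20 − 2.1 = 17.9 | 20 − 3.5 = 16.5 |
| 0.50 | 20 − 4.2 = 15.8 | 20 − 7.0 = 13.0 |
| 0.75 | 20 − 6.3 = 13.7 | 20 − 10.5 = 9.5 |

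In simulations at shifts of 0.25, 0.5 and 0.71 SD (5,000 runs each), such a variable passed the screen in 84-100% of trials. The share of trials with a significant adjusted effect fell from about 0.79 to 0.72-0.75, 0.52-0.61 and 0.31-0.49 respectively.

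The direction depends on the sign. If the variable moves against the effect, for example more analgesia given in one arm and less pain as a result, the same formula raises the estimate. At a = 0.5 and r = −0.3 it is 20 + 0.3 × 28 × 0.5 = 24.2. The pass rates above do not apply to that case.

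**6. The condition.** If *observed* is read as significant, the trials that reach adjustment have a mean unadjusted difference of about 22.4 against a true 20. If it is read as any non-zero difference, the condition excludes almost nothing. The plan does not say which is meant.

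**The case against.** The strongest reply is that the main result is not exposed. The sample size rests on an unadjusted t-test, the unadjusted comparison comes first, and the adjusted step is worded as exploration. This stands. A reader might infer that the adjusted model could overturn a correct primary result, but no rule in the plan lets it replace or veto the unadjusted test.

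A second reply is that the pool is meant to be baseline only. The same section uses demographic and clinical covariates for its check on the success of randomisation, which makes sense only for baseline data. Measures for Aim 2 lists intraoperative and PACU opioids as outcome data, and Hypothesis 2 predicts differences at 24, 48 and 72 hours, not in theatre or PACU. This largely stands. A reader might infer that the plan intends to adjust for on-treatment variables, and the documents do not say so. They do not exclude it either, and type of anesthesia is not an Aim 2 measure. A short part of the document after the statistical section was not available, so a covariate list there cannot be ruled out.

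Third, the baseline-only harm is small. The screen still beats no adjustment, does not inflate type I error, and rarely loses a predictor with r of 0.4 or more. The fixed-set benchmark assumes the two real predictors are known. All of this is correct and limits the size of the point. It does not justify keeping a rule that a fixed list improves on at almost no cost.

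Finally, *observed* need not mean significant, and the condition cannot create a false positive in the main test. That is also correct; what remains is selective reporting of adjusted results under an undefined trigger.

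**Conclusion.** The point holds for the adjusted analysis. Its covariate set is chosen by the data, it is run only when a difference has been observed, it need not contain the stratification factor, and it is not protected from post-assignment variables. The main unadjusted comparison is unaffected.

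For baseline covariates the loss is modest: roughly one predictor in five missed at r about 0.3, and about 2 to 4 points of power against a fixed set of two real predictors. If a post-assignment variable entered, the adjusted effect could be about 9 to 18 instead of 20 under shifts of 0.25-0.75 SD and r of 0.3-0.5, or above 20 if the signs are opposed. Those shifts and correlations are assumptions, and entry itself rests on the plan's silence. It would go too far to say that adjustment will shrink a real effect; the supported statement is that it could bias the adjusted estimate in either direction. The wording should be changed before analysis.

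**What to change.** Delete the p≤0.1 entry rule and the condition that a difference be observed. For each outcome, pre-specify one adjusted model: ANCOVA or a mixed model for continuous outcomes, and a matching regression for categorical ones. Each model should contain the randomisation stratum (anticipated POD 1 pain, 4-6 versus above 6) and a short fixed list of pre-randomisation covariates. State that it will be reported whatever the unadjusted result, and that nothing measured after assignment may enter. The bivariate screens can stay as labelled exploration.

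The cost is a few sentences of plan wording. No new data are needed and the sample size does not change. The downside is a few degrees of freedom if a listed covariate proves uninformative.
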